- All participants have completed Week 72 (ie, 24 weeks after completion of investigational intervention at Week 48), or discontinued earlier.
- All participants have completed Week 96 (ie, 48 weeks after completion of investigational intervention at Week 48), or discontinued earlier.

One additional IA may be performed at the sponsor's discretion when all participants, who completed NA treatment at Week 48 of follow-up, have completed Week 120, ie, Week 24 of the extended follow-up, or discontinued earlier, to support interactions with health authorities.

All IAs will be performed by the sponsor because occurring after the primary analysis, which will be conducted at the time when all participants have completed Week 48 or discontinued earlier. Both primary and interim analyses will be based on all data available at the predefined cut-off time, including data at later time points for those participants who have reached subsequent visits.

Independent Data Monitoring Committee

An IDMC will be established for continuous monitoring of SAEs, AEs leading to discontinuation, and ALT flares. In addition, the IDMC will review the unblinded results of the efficacy parameters measured by different HBV disease blood markers (eg, HBV DNA, HBeAg, HBsAg, etc).

The IDMC will have access and use the totality of unblinded results to make recommendations, including all safety and efficacy assessments available at a given interim milestone. Possible recommendations include, but are not limited to, stopping the study or any of the study interventions for safety concerns. The Sponsor Committee will review the time course of the different HBV disease blood markers to make further decisions. Decision rules will be detailed and listed in the IDMC charter and will be non-binding.

Independent Flare Expert Panel

[figure not shown]
An IFLEP will also be appointed. The IFLEP is composed of 3 independent medical experts with experience and expertise in hepatitis B and its treatment. The IFLEP will monitor ALT flares and will make recommendations regarding flare management based on an analysis of aggregate data.

In order to allow for an unbiased assessment, members of the committee will not serve as study investigators or as members of the IDMC and will be blinded to the treatment assigned to each participant.

Further details on the IFLEP process will be included in the IFLEP charter.

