- With confirmed* post-treatment increases in HBV DNA >2,000 IU/mL and ALT >5x ULN.
- With confirmed* post-treatment increases in HBV DNA >20,000 IU/mL.

Note: Additional re-testing and/or earlier restarting of NA treatment is at the investigator's discretion, even if the above cut-offs are not yet met.

To avoid delays in decision making, sites are encouraged to run local re-testing in parallel with central retesting in the situations described above that require more frequent re-testing. Local test results are to be recorded in the CRF and/or source documents, including information on the HBV DNA assay used. In

^{*} At least 4 weeks apart – frequency of visits as described above

addition, to avoid delays in NA re-treatment, it should be considered to dispense NA to participants who potentially met the NA re-treatment criteria (eg, pending confirmation) and who will not be available to come to the study site immediately at the time the confirmatory test results will become available. This should ensure that the participant can immediately re-start NA treatment if indicated, upon direct confirmation by the investigator.

In case NA treatment is re-started, participants will be followed until the end of the study or until clinical stabilization, whichever comes later.

Management of intervention-emergent ALT/aspartate aminotransferase (AST) elevations is discussed below.

NUMBER OF PARTICIPANTS

A target of 450 male and female participants will be randomized.

Description of Interventions

Intervention name	JNJ-3989	Placebo for JNJ-3989	JNJ-6379	Placebo for JNJ-6379	Entecavir (ETV) monohydrate	Tenofovir disoproxil fumarate (TDF)	Tenofovir alafenamide (TAF)***
Dosage formulation	Solution for injection	Solution for injection	Tablets	Tablets	Film-coated tablets	Film-coated tablets	Film-coated tablets
Unit dose strength(s)	200 mg/vial	0.9% saline	25 and 100 mg		0.5 mg	300 mg**	25 mg
Dosage regimen	100 mg once every 4 weeks (Arms 1 and 3) 200 mg once every 4 weeks (Arm 2) 40 mg once every 4 weeks (Arm 4)	0.5 mL once every 4 weeks (Arms 5 and 6)	250 mg qd (Arms 1 and 5)	qd (Arms 2, 3, 4, and 6)	Nucleoside-naïve patients: 0.5 mg qd Lamivudine- refractory patients: 1 mg* qd (but should preferably be treated with TDF or TAF instead)	300 mg qd	25 mg qd
Route of administration	Subcutaneous injection (in the abdomen)	Subcutaneous injection (in the abdomen)	Oral	Oral	Oral	Oral	Oral

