Safety and tolerability will be assessed throughout the study from the time that the informed consent form is signed until completion of the last study-related activity, which may include contact for follow-up of safety. The evaluations of safety and tolerability will include monitoring of (S)AEs, physical examinations (including body weight), vital signs measurements, triplicate 12-lead ECGs, and clinical laboratory tests (including hematology, blood biochemistry, blood coagulation, urinalysis, urine chemistry, and renal biomarkers). Any clinically relevant changes occurring during the study must be recorded in the AE section of the case report form.

Specific toxicity management plans in line with the known pharmacological profile of the study intervention (and the drug classes) evaluated in this study are implemented.

Management of Intervention-emergent ALT/AST Elevation

Elevated liver enzyme activity can be triggered by the underlying HBV disease as well as by the study intervention.

Any intervention-emergent elevation of ALT and/or aspartate aminotransferase (AST) $\ge 3x$ ULN and $\ge 3x$ nadir (ie, lowest value during study participation) should trigger an assessment of confounding factors (alcohol intake, change in concomitant medication, and comorbidities) and should trigger a confirmatory study visit to repeat laboratory testing of AFP, ALT, AST, alkaline phosphatase (ALP),

bilirubin (total and direct), INR, albumin, and HBV DNA. The confirmatory visit should be scheduled as soon as possible, preferably within 7 days of the receipt of the initial ALT/AST results. In case the repeat laboratory testing shows an isolated ALT/AST elevation (ie, with stable albumin, bilirubin [total and direct], and INR) the participant may continue study intervention. In case of confirmed ALT elevation >1,000 U/L, investigational intervention should be discontinued. In both cases, NA treatment should be continued. The participant will be monitored on a weekly basis until ALT and/or AST levels have returned to 50% of the maximal value.

If the ALT and/or AST level is $\ge 3x$ ULN and $\ge 3x$ nadir and is associated with any of the following laboratory results or clinical symptoms:

- INR ≥1.5, OR
- direct bilirubin >1.5x ULN, OR
- serum albumin <3.0 g/dL, OR
- ascites, hepatic encephalopathy, or liver-related symptoms (eg, severe fatigue, nausea, vomiting, right upper quadrant pain in the absence of an alternative medical explanation), OR

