- m. At Week 48 or at time of early discontinuation, it will be communicated to the investigators whether the participants were allocated to either an investigational arm (Arms 1 to 5) or the control arm (Arm 6). Only at Week 72, randomization codes (for Arms 1 to 5) will be fully disclosed to the investigators. The sponsor will be fully unblinded for the primary analysis at Week 48.
- n. In between study visits, participants will take oral study intervention at home and they will bring their study intervention with them to each study visit. At study visits, the study intervention should be taken on site.
- o. NA will be dispensed at Week 48 in case the participant does not meet the NA treatment completion criteria.
- p. If the NA treatment completion criteria are met based on clinical laboratory tests performed at Week 44, treatment with NA will be completed at Week 48.
- q. Complete physical examination, including height (at screening only), body weight, skin examination, and other body systems.
- r. Symptom-directed physical examination, including body weight.

- s. Vital signs include supine SBP, DBP, pulse rate, and body temperature.
- t. All ECGs will be read centrally. Only on Day 1, an ECG will be collected and assessed locally prior to dosing.
- u. Biochemistry samples must be taken after fasting for at least 10 hours for measurement of phosphate, calcium, creatinine, and lipids.
- v. Creatinine clearance (eGFR calculated by the CKD-EPI formula) will be assessed.
- w. Intervention-emergent ALT/AST elevations (ie, ALT and/or AST ≥3x ULN and ≥3x nadir [ie, lowest value during study participation]), should trigger an assessment of confounding factors (alcohol intake, change in concomitant medication, and comorbidities) and a confirmatory visit, to be scheduled preferably within 7 days of the receipt of the initial ALT/AST results, to repeat laboratory testing of AFP, ALT, AST, ALP, bilirubin (total and direct), INR albumin, and HBV DNA. Additional tests should be considered based on clinical judgement. For more details and further management guidance refer to Section 8.3.6.1 Intervention-emergent ALT/AST Elevations and Section 10.6 Appendix 6: Intervention-emergent ALT/AST Elevations.
- x. Urine chemistry sample (quantitative measurement): creatinine, sodium, phosphate, glucose, protein, and albumin.

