^{*} At least 4 weeks apart frequency of visits as described above

confirmatory test results will become available. This should ensure that the participant can immediately re-start NA treatment if indicated, upon direct confirmation by the investigator.

In case NA treatment is re-started, participants will be followed until the end of the study or until clinical stabilization, whichever comes later.

NA re-treatment criteria and monitoring after stopping of NA are presented graphically in Section 10.14, Appendix 14.

Management of intervention-emergent ALT/AST elevations is discussed in Section 8.3.6.

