7. DISCONTINUATION OF STUDY INTERVENTION AND PARTICIPANT DISCONTINUATION/WITHDRAWAL

7.1. Discontinuation of Study Intervention

A participant's investigational intervention **must** be discontinued if any of the criteria listed below apply. In those cases, NA treatment may be continued or, in consultation with the sponsor, discontinued based on investigator judgement or completed based on the NA treatment completion criteria (see Section 6.6).

- The investigator believes that for safety or tolerability reasons (eg, AE) it is in the best interest of the participant to discontinue investigational intervention.
- The participant becomes pregnant.
- The participant has a ≥grade 3 rash (see Section 10.5, Appendix 5, Rash Management) or allergic reaction (see Section 8.3.6.3).
- The participant has signs of hepatic decompensation (ie, clinical evidence of ascites, bleeding varices, or hepatic encephalopathy).
- The participant has a confirmed ≥grade 3 estimated glomerular filtration rate (eGFR) abnormality and a drop from baseline of >10 mL/min/1.73 m², considered at least possibly related to JNJ-3989 or JNJ-6379. Change of NA treatment should be considered anytime, according to the prescribing information. (see Section 8.3.6.4).
- The participant has a confirmed QTcF prolongation (defined as a QTcF value of >500 ms, or an increase from baseline of >60 ms) at any given time point.

- The participant requires ≥7 days of treatment with any of the disallowed medications listed in Section 6.5 and does not intend to discontinue treatment with the disallowed medication.
- The participant has confirmed HBV virologic breakthrough (ie, confirmed on-treatment HBV DNA increase by >1 log₁₀ IU/mL from nadir or confirmed on-treatment HBV DNA level >200 IU/mL in participants who had HBV DNA level <LLOQ of the HBV DNA assay). In case of virologic breakthrough, changing the NA should be considered in consultation with the sponsor.
- The participant has ALT/AST elevations, as described in Section 8.3.6.1, Interventionemergent ALT/AST Elevations.

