8.3.6.1. Intervention-emergent ALT/AST Elevations

Elevated liver enzyme activity can be triggered by the underlying HBV disease as well as by the study intervention.

Management of intervention-emergent ALT/AST elevations is presented graphically in Section 10.6, Appendix 6: Intervention-emergent ALT/AST Elevations, and is described below.

Any intervention-emergent elevation of ALT and/or AST $\ge 3x$ ULN and $\ge 3x$ nadir (ie, lowest value during study participation) should trigger an assessment of confounding factors (alcohol intake, change in concomitant medication, and comorbidities) and should trigger a confirmatory

study visit to repeat laboratory testing of AFP, ALT, AST, ALP, bilirubin (total and direct), INR, albumin, and HBV DNA. Additional tests should be considered based on clinical judgement (refer to Section 10.6, Appendix 6: Intervention-emergent ALT/AST Elevations). The confirmatory visit should be scheduled as soon as possible, preferably within 7 days of the receipt of the initial ALT/AST results. In case the repeat laboratory testing shows an isolated ALT/AST elevation (ie, with stable albumin, bilirubin [total and direct], and INR) the participant may continue study intervention. In case of confirmed ALT elevation >1,000 U/L and >3x the baseline value, investigational intervention should be discontinued. In both cases, NA treatment should be continued. The participant will be monitored (laboratory testing of ALT, AST, ALP, bilirubin [total and direct], INR, albumin, and HBV DNA) on a weekly basis until ALT and/or AST levels have returned to 50% of the maximal value.

If the ALT and/or AST level is $\ge 3x$ ULN and $\ge 3x$ nadir and is associated with any of the following laboratory results or clinical symptoms:

- INR \geq 1.5, OR
- direct bilirubin >1.5x ULN, OR
- serum albumin <3.0 g/dL, OR
- ascites, hepatic encephalopathy, or liver-related symptoms (eg, severe fatigue, nausea, vomiting, right upper quadrant pain in the absence of an alternative medical explanation), OR
- other indication of reduced liver function

the participant should discontinue investigational intervention and should be monitored on a weekly basis or as per good clinical practice until ALT and/or AST levels have returned to 50% of the maximal value and, if present, liver-related symptoms have improved. NA treatment should be continued. Additional tests can be considered based on clinical judgement.

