8.3.6.5 Hematologic Abnormalities		finding, any relevant abnormalities			
		in hematologic parameters will be			
		carefully monitored to trigger a			
		mandatory higher visit frequency in			
		case of significant on-treatment			
		reduction in hematologic parameters			
		to ensure closer follow-up.			
2.2.1 JNJ-3989 and JNJ-6379	Preclinical update: Addition of	Preliminary results of the 3-month			
2.2.2.1 Overall Nonclinical	preliminary results from 3-month	combination toxicity study with			
Assessment of the Combination	combination toxicity study with	JNJ-6379 and JNJ-3989 in the rat			
Therapy	JNJ-3989 and JNJ-6379	include an update on the sacrifice of			
		one male rat receiving JNJ-6379			
		orally at 100 mg/kg/day and			
		JNJ-3989 subcutaneous at 60 mg/kg			
		related to bone marrow depletion			
		with pancytopenia including marked			
		thrombocytopenia.			
10.2. Appendix 2: Clinical	Addition of reticulocyte count and	To allow for early detection of			
Laboratory Tests	reticulocyte index to all study visits	changes in hematologic parameters.			

Clarifications, Additions, and Corrections			
Section Number and Name Description of Change Brief Rationale			
1.3.1 Schedule of Activities –	ECG at baseline needs to be	Clarification	
Screening and Study Intervention	performed and assessed locally prior		
Phase	to dosing but is not part of eligibility		

CONFIDENTIAL – FOIA Exemptions Apply in U.S.

Clarifications, Additions, and Corrections				
Section Number and Name	Description of Change	Brief Rationale		
	criteria assessed after screening.			
1.3.1 Schedule of Activities – Screening and Study Intervention Phase 1.3.2 Schedule of Activities – Follow-up Phase 10.6 Appendix 6: Intervention- emergent ALT/AST Elevations	Add alpha-fetoprotein measurement every 24 weeks and at the time of ALT flares	Alpha-fetoprotein is of interest to link to liver ultrasound assessment for the screening of HCC every 6 months. In addition, alpha-fetoprotein has been reported to be associated with HBsAg decline. Thus, it is relevant to assess this marker.		
8.3.6.1 Intervention-emergent ALT/AST Elevations 10.2 Appendix 2: Clinical Laboratory Tests	Added wording for ALT/AST elevations management, added baseline value as reference for stopping criteria, and ensure that all relevant liver tests are performed	For closer patient safety monitoring and management		

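### The Synopsis and Section 8.3.6.1 give different ALT thresholds for stopping investigational intervention; the overlap is narrow, but one rule should apply

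*Protocol*

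**What the plan says.** The Synopsis, under management of intervention-emergent ALT/AST elevation, states: "In case of confirmed ALT elevation >1,000 U/L, investigational intervention should be discontinued". Section 8.3.6.1 has the same sentence with one more condition: "In case of confirmed ALT elevation >1,000 U/L and >3x the baseline value, investigational intervention should be discontinued".

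The surrounding text is otherwise closely parallel. In both places the pathway opens when ALT and/or AST is at least 3x ULN and at least 3x nadir, nadir being the lowest value on study. Both let a participant with an isolated elevation (albumin, bilirubin and INR stable) stay on study intervention. Both stop investigational intervention if an INR, direct bilirubin, albumin or symptom criterion, or another sign of reduced liver function, accompanies the elevation.

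Several passages direct the reader to the body text:
- Section 7.1 lists among its mandatory stops: "The participant has ALT/AST elevations, as described in Section 8.3.6.1". It gives no ALT threshold of its own.
- The Schedule of Activities (1.3.1 footnote w, repeated in the 1.3.2 footnote on ALT/AST elevations) says: "For more details and further management guidance refer to Section 8.3.6.1 Intervention-emergent ALT/AST Elevations".
- Section 6.7 says: "Management of intervention-emergent ALT/AST elevations is discussed in Section 8.3.6".

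The Synopsis refers to its own wording instead: "Management of intervention-emergent ALT/aspartate aminotransferase (AST) elevations is discussed below". Section 8.3.6.1 adds: "Management of intervention-emergent ALT/AST elevations is presented graphically in Section 10.6". That Appendix 6 graphic is not in the text supplied for review.

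**The concern.** A site that works from the Synopsis and a site that works from Section 8.3.6.1 could treat the same isolated, confirmed ALT value differently. Under the Synopsis the participant should stop. Under 8.3.6.1 the extra condition is not met and the participant may continue.

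Reporting is touched as well. SAP 4.5 counts meeting withdrawal criteria without being withdrawn as a type of protocol deviation, and SAP 5.4.14.1 summarises on-treatment biochemical flares that led to discontinuation by arm. Neither can be judged consistently for a participant in the disputed band until one threshold is fixed.

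**Working it through.** No figure in the plan depends on this point, so there is nothing to reproduce. The check is where the two rules part.

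**Inputs**
- Synopsis rule: confirmed ALT > 1,000 U/L.
- Section 8.3.6.1 rule: confirmed ALT > 1,000 U/L and ALT > 3 × baseline.
- Shared trigger, both passages: ALT and/or AST ≥ 3 × ULN and ≥ 3 × nadir.
- Screening ALT limits, Protocol 5.1: < 10 × ULN if not currently treated (criterion 4b); ≤ 2 × ULN if virologically suppressed (criterion 5c).
- ULN: not stated. Assumed 30 to 50 U/L below.

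**Step 1: the band.** Any case that meets the 8.3.6.1 rule also meets the Synopsis rule. They part only when 1,000 < ALT ≤ 3 × baseline. This needs baseline > 1,000 / 3 = 333.3 U/L.

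**Step 2: the nadir condition.** If the shared trigger governs the sentence, ALT ≥ 3 × nadir is also required, so nadir ≤ ALT / 3 ≤ baseline. Unless ALT is exactly 3 × baseline, some other on-study value must lie below baseline. In practice ALT has fallen and then rebounded. This narrows the band but does not empty it.

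**Step 3: who can reach it on the screening limits.**
- Not currently treated: 10 × ULN must exceed 333.3, so ULN > 33.3 U/L.
- Virologically suppressed: 2 × ULN must exceed 333.3, so ULN > 166.7 U/L, far above the assumed range.

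For participants not currently treated:

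| Assumed ULN (U/L) | Highest admissible baseline, 10 × ULN | Baseline range in the band (U/L) | As a multiple of ULN | ALT range in the band (U/L) |
|---|---|---|---|---|
| 30 | 300 | none (3 × 300 = 900) | none | none |
| 35 | 350 | 333 to 350 | 9.5 to 10 | 1,000 to 1,050 |
| 40 | 400 | 333 to 400 | 8.3 to 10 | 1,000 to 1,200 |
| 50 | 500 | 333 to 500 | 6.7 to 10 | 1,000 to 1,500 |

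The limits apply at screening, so a Day 1 baseline could fall outside them.

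**Step 4: an example.** Take baseline 360 U/L (9 × an assumed ULN of 40) and a confirmed, isolated ALT of 1,050 U/L. The ratio to baseline is 1,050 / 360 = 2.9. The nadir condition holds if any on-study value was at or below 1,050 / 3 = 350 U/L. The Synopsis says stop; the 8.3.6.1 criterion is not met.

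**Step 5: what still stops such a participant under either text.** The accompanying liver criteria stop treatment in both passages, and the first item of Section 7.1 requires a stop when the investigator judges it best for the participant's safety.

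**The case against.** The strongest reply is that the operative text can be identified. The mandatory list in 7.1, both Schedule footnotes and 6.7 lead to 8.3.6 or 8.3.6.1, and nothing outside the Synopsis sends a reader to the Synopsis for this rule. The Synopsis's own pointer mirrors the sentence in 6.7 with the section number left out, which looks like drafting style. The Amendment 2 entry in the amendment history records "added baseline value as reference for stopping criteria" against 8.3.6.1 and Appendix 2, not the Synopsis, which suggests a summary that was not updated. Stopping at the lower bar also breaches neither passage, since 8.3.6.1 permits continuation and does not demand it.

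Much of this stands. It explains how the texts came to differ and limits the consequences: they disagree on whether a stop is called for, and no site faces incompatible commands. But the supplied text has no precedence clause, the Synopsis states the rule in full, and an amendment log does not decide which current sentence governs.

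Three stronger readings are tempting and are not supported.
- A reader might infer a second contradiction about NA, because 7.1 and 4.1 let NA be stopped on investigator judgement in consultation with the sponsor, while 8.3.6.1 says to continue it. The former is a general default beside an event-specific rule, and continuing NA satisfies every version.
- A reader might infer that the Appendix 6 graphic is a third version. It was not available, and 8.3.6.1 describes it as showing the same management.
- A reader might infer a definite shift in the primary endpoint. The verdict states why that is only conditional.

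**Conclusion.** The inconsistency is real: two current passages set different ALT thresholds for stopping investigational intervention. Expected impact is low. Disagreement needs a baseline above about 333 U/L, a confirmed ALT above 1,000 U/L but at most 3x baseline, no other stopping criterion met and, if the shared trigger governs, a preceding fall. On the screening limits that confines it to participants not currently treated, and only if the ULN exceeds about 33 U/L. The number in the band cannot be derived from the documents and may be zero.

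Any effect on the primary endpoint is conditional. SAP 5.2.2 makes a participant who discontinued treatment before Week 44 a non-responder, but does not say whether stopping the study agents alone, with NA continued, counts. SAP Section 2 defines study treatment to include NA and study agent to exclude it. Only if such a stop counts, falls before Week 44, and concerns someone who would otherwise have met all four Week 44 criteria would one participant move an arm's rate: by 1/90 = 1.1 or 1/45 = 2.2 percentage points at the planned arm sizes. Enrollment was extended by about 5% (SAP 1.4), so these are approximate.

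**What to change.** Reconcile the Synopsis with Section 8.3.6.1, and check the Appendix 6 graphic against both, so that one threshold applies throughout. Which threshold that is belongs to the sponsor's clinical team; this review does not choose.

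Investigational dosing appears to be complete: SAP Amendment 2 mentions interim analyses already done, and Protocol 9.5 places every interim analysis after the Week 48 primary analysis. If so, record which rule sites applied and list any participants whose confirmed ALT exceeded 1,000 U/L but was no more than 3x baseline.

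The cost is a wording change or clarifying memo, or a short note with one listing that may be empty. Sample size, alpha and the analysis methods are unaffected.
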